9.2.1. Dose-Escalation Phase

Dose escalation will be driven by safety using a modified 3+3 scheme, with incorporation of model-based dose escalation (Neuenschwander et al. 2008) to assist in estimation of DLT rate at recommended dose level.

A model-based method that incorporates prior expectations about the dose-toxicity curve and controls for over-dosing probability will be applied to the data at the end of each cohort, which will provide quantitative guidance to the investigators and Lilly CRP to help determine the next dose level. Prior expectations about the dose-toxicity curve will be based on observed DLT rates in Study JJCA. After incorporation of observed DLT rates in this study, the posterior probability of a DLT at each dose level will be categorized to 4 bands:

- under-dosing: the probability of a DLT at a given dose level in (0, 0.20)
- targeted toxicity: the probability of a DLT at a given dose level in (0.20, 0.35)
- excessive toxicity: the probability of a DLT at a given dose level in (0.35, 0.60)
- unacceptable toxicity: the probability of a DLT at a given dose level in (0.60, 1.00)

The model aims to recommend a dose which maximizes the probability of targeted toxicity, while controlling the probability of excessive or unacceptable toxicity to less than 25%. The maximum increment of escalation will be no more than 100%. The exact increment will be determined by the investigators and Lilly CRP and may be less than the model prediction or <100%.

Each dose level will have a minimum of 3 patients enrolled concurrently to it. If 1 patient experiences a DLT, then additional patients can be enrolled to that cohort provided the observed DLT rate dose does not exceed 33%.

Additional patients may be enrolled at a specific dose level to characterize PK/PD, provide that dose level does not exceed the MTD

In case more than 3 patients have been consented concurrently, the additional patients may be treated. The decision about which dose level the patient will be treated at will be made after discussion between the CRP/study team and the investigators. The decision will be documented.

Once the MTD has been identified, a discussion between the sponsor and investigators may occur in order to treat additional patients at intermediate doses below the MTD.

Safety data, in particular AEs, will be the primary criteria to allow for the dose escalation. The dose will be escalated following assessment of toxicity using the standard scoring system, CTCAE v 4.0, established by the NCI. Any AEs related to LY3039478 and/or dexamethasone will be considered as toxicities.

If available at the time of the dose-escalation decision, PK (eg, maximum observed concentration [C_{max}], AUC, and apparent systemic clearance) and PD results will be used as secondary/supporting data for dose escalation. No dose escalation can occur without prior discussion and agreement between the investigator and the Lilly CRP. The decision will be documented in writing. Intrapatient dose escalations are not permitted.

Based on the ongoing safety reviews, modifications to the dose-escalation strategy or other design elements may be made via protocol amendment to ensure patient safety.

[Table JJCB.9.2](#) shows the proposed dose levels for LY3039478 in combination with dexamethasone for the adult cohort. The starting dose level of 50 mg of LY3039478 was defined from Study JJCA and data will be evaluated on an ongoing basis until the MTD is determined. If the starting dose exceeds the MTD, a LY3039478 dose level (-1) may be explored. It should be noted that although an example escalation table is shown in [Table JJCB.9.2](#), alternate doses may be selected. Intermediate dose levels will be explored if deemed necessary after discussion between the sponsor and investigators and taking into account patient safety and PK/PD information.

Table JJCB.9.2. Proposed LY3039478 Dose-Escalation Scheme for the Adult Cohort

Dose Level	LY3039478 Dose (mg)	Dexamethasone Dose (mg)
-1 ^a	25	24
1	50	24
2	75	24

^a Dose level -1 to be used only in the event of dose-limiting toxicities experienced in dose level 1 necessitating a dose de-escalation.

The starting dose for pediatric cohort will be defined upon safety assessment of adult cohort. The starting dose will be 80% of total adult dose. Pediatric patients will be dosed based on BSA. Dose escalation will follow similar scheme to adult cohort.

By nature of being a dose-escalation study, data will be evaluated on an ongoing basis until the MTD is determined, as defined below.

9.2.2. Dose-Limiting Toxicity Determination and Maximum Tolerated Dose Definition

Disease-related myelosuppression is typical in the setting of T-ALL/T-LBL. Therefore, myelosuppression will not be included in the definition of a DLT, unless it fits the criteria outlined below.

A DLT is an AE observed during the first 28-day cycle (when patients receive LY3039478 and dexamethasone) that is determined by the investigator to be at least possibly related to LY3039478 according to CTCAE v 4.0 and fulfills any of the following criteria:

- \geq CTCAE Grade 3 nonhematological toxicity. Exceptions will be made for:
 - Grade 3 nausea, vomiting, or constipation that lasts less than 72 hours and that can be controlled with treatment
 - Grade 3 electrolyte disturbance that can be controlled with treatment and persists less than 5 days
 - Grade 3 hyperglycemia or Grade 4 hyperglycemia without ketoacidosis during and after the end of dexamethasone treatment unless it is not controlled by oral medication or insulin before the start of the next dexamethasone round
 - Grade 3 arterial hypertension during and after the end of dexamethasone treatment unless it is not controlled by oral medication before the start of the next dexamethasone round
 - tumor lysis syndrome (TLS): patients who demonstrate a clinical syndrome consistent with TLS and have transient (<7 days) and manageable Grade 3 abnormalities in serum electrolytes, renal function and/or chemistries (ie, uric acid, potassium, phosphorus, calcium, creatinine, blood urea nitrogen, etc.)
 - Grade 3 diarrhea for <5 days and unless it cannot be controlled with standard treatment
 - transient (<7 days) Grade 3 elevations of ALT and/or AST, that are not accompanied by a Grade 2 bilirubin increase are considered an exception to the DLT criteria, unless there is a clear alternative cause (eg, worsening biliary obstruction) if agreed by the study investigator and Lilly CRP
- any other significant toxicity deemed by the primary investigator and Lilly clinical research personnel to be dose limiting (eg, any toxicity that is possibly related to the study medication that requires the withdrawal of the patient from the study during Cycle 1)

A dose-limiting equivalent toxicity (DLET) is defined as an AE occurring between Day 1 and Day 28 of any cycle (other than Cycle 1) for a patient enrolled in the Phase 1 portion or in any cycle (including Cycle 1) for a patient enrolled in the Phase 2 portion that would have met the criteria for DLT if it had occurred during Cycle 1 for a patient enrolled in the Phase 1 portion.

MTD is defined as the highest explored dose level for which the probability of DLT does not exceed 33%. For the recommended Phase 2 dose, the rate and nature of AEs observed beyond the first cycle of treatment will be considered.

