No mortality was observed in the 1-month dog toxicity study. Substantial decreases in body weight and food consumption occurred early in the study at 0.3 and 1 mg/kg/dose and resulted in supplemental food being offered to all dogs at these dose levels. Clinical signs were limited to fecal changes including soft, watery, mucoid, and discolored feces in dogs administered 0.3 and 1 mg/kg/dose. Fecal changes at 0.1 mg/kg/dose were less frequent and less severe than at higher doses. These changes were consistent with the dose-dependent mucoid enteropathy that was evident histologically in the small and large intestines at all doses and was considered to be adverse at ≥ 0.3 mg/kg/dose based on the presence of concurrent mucosal degeneration/necrosis at these mid and high doses. Generalized lymphoid depletion occurred in multiple tissues including the thymus, spleen, mesenteric lymph nodes, and/or gut-associated lymphoid tissue. Hypercellularity of the bone marrow (femur and sternum) at 1 mg/kg/dose correlated with hematology findings including increased total leukocytes, likely associated with inflammation in the large and small intestines. Increased thickness of the hypertrophy zone was also evident in cartilage of the rib and sternum at 1 mg/kg/dose, which was similar but more subtle than the finding in the rat. The MTD and HNSTD in this dog study was 1 mg/kg, the highest dose tested. Additional details and findings from this study are presented in the compound's IB.

Thrombocytopenia was identified as a DLT in a few Phase 1 patients (see Section 5.1.6) however no effects on platelets were noted in the 1-month rat or dog toxicology studies.

Based on in vitro hERG results, there is no expected risk for QT prolongation by hERG inhibition. In the 1-month dog study, no test article-related effects were observed in any of the electrocardiogram (ECG) parameters (heart rate, RR interval, PR interval, QRS duration, QT interval, and corrected QT [QTc] interval). No evidence of mutagenicity was observed in a bacterial mutagenicity (Ames) assay. In additional in vitro assays, LY3039478 was classified as a nonirritant and demonstrated no phototoxic potential.

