5.1.6. Clinical Experience with LY3039478

As of April 2014, validated data from 39 patients in the first-in-human dose (FHD) Study I6F-MC-JJCA (JJCA) treated with LY3039478 in doses ranging from 2.5 mg to 60 mg are available. As of November 2014, LY3039478 doses of up to 100 mg have been explored. The MTD has been determined to be 75 mg.

Dose-limiting toxicities (DLTs) observed at dose levels of 20 mg, 30 mg, and 60 mg LY3039478 were thrombocytopenia Grade 4 in 1 patient in each dose group. Dose limiting toxicities at 100 mg included Grade 3 nausea (not manageable by medical treatment) and Grade 3 asthenia. In addition, 1 patient at 100 mg experienced Grade 2 colitis.

The most common adverse events (AEs) (>5% of patients) assessed as possibly related to study drug by the investigator included vomiting (41.0%); diarrhea (30.8%); asthenia, nausea, and hypophosphatemia (28.2%, each); decreased appetite (17.9%); hair color changes (15.4%); weight decreased (12.8%); thrombocytopenia, mucosal inflammation, alanine aminotransferase (ALT) increased, dry skin, and skin fissures (10.3% each); stomatitis and aspartate aminotransferase (AST) increased (7.7%, each); eyelash discoloration, dyspepsia, lipase increased, and dysgeusia (5.1%, each).

No Grade 5 Common Terminology Criteria for Adverse Events (CTCAE) events that were possibly related to study drug were reported. Grade 4 events possibly related to study drug included thrombocytopenia (3 patients, 7.7%) and increased lipase (1 patient, 2.6%). Grade 3 events possibly related to study drug included hypophosphatemia (5 patients, 12.8%) and colitis, asthenia, weight loss, and anorexia (1 patient each, 2.6%).

More information about the known and expected benefits, risks and reasonably anticipated AEs of LY3039478 can be found in the compound's IB. Information on AEs expected to be related to the investigational product can be found in Section 7 (Development Core Safety Information [DCSI]) of the IB. Information on serious adverse events (SAEs) expected in the study population independent of drug exposure and assessed by the sponsor in aggregate, periodically during the course of the study, can be found in Section 6 (Effects in Humans) of the IB.

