9.4.2. Dose Adjustments for LY3039478 between Cycles

Before the start of each cycle, nonhematological toxicities (except alopecia and fatigue) must resolve to baseline. The start of LY3039478 may be delayed up to 21 days to allow sufficient time for recovery. Patients experiencing non-transient Grade 4 nonhematological toxicity or not recovering from toxicity within 21 days should be discontinued from the study.

The dose of LY3039478 should be reduced to the dose level administered in the previous cohort for all subsequent cycles of therapy if the investigator determines that it is in the best interest of the patient or if the patient experienced at least 1 of the following events:

- DLT (in Cycle 1 for patients in Phase 1)
- DLET (in Cycle 2 or beyond for patients in Phase 1, or in any cycle for patients in Phase 2)
- omission of more than 7 doses of LY3039478 in a single cycle for tolerability

For patients requiring a dose reduction, re-escalation to the original dose level is not permitted.

A second dose reduction is allowed only for patients treated at adult dose level ≥ 75 mg or pediatric equivalent (dose may be reduced to 25 mg or pediatric equivalent). Dose reduction by more than 2 dose levels is not permitted; patients requiring dose reduction by more than 2 dose levels should be discontinued from the study.

If a patient experiences a DLET at the second reduced dose level, then the patient will be discontinued from the study. If a patient requires omission of more than 3 doses for tolerability at the reduced dose levels, then treatment may continue if the investigator determines that the patient is receiving clinical benefit.

In the Phase 2 portion of the study, investigators will treat all patients as if the patient is receiving active study drug, LY3039478, and will adjust doses accordingly.

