10.3.1. Adverse Events

Lilly has standards for reporting AEs that are to be followed regardless of applicable regulatory requirements that may be less stringent. A clinical study AE is any untoward medical event associated with the use of a drug in humans, whether or not it is considered related to that drug.

However, leukemia-related hematologic effects should not be reported as AEs. Because Grade 3 or 4 myelosuppression (leukopenia, neutropenia, thrombocytopenia, and anemia) is expected in

the setting of relapsed T-ALL, these cytopenias will not be considered AEs for the purpose of this study, unless the investigator classifies them as AEs based on clinical circumstances.

Lack of drug effect is not an AE in clinical trials, because the purpose of the clinical trial is to establish drug effect.

Any clinically significant findings from ECGs, laboratory values, vital sign measurements, other procedures, and so on that result in a diagnosis should be reported to Lilly or its designee.

Cases of pregnancy that occur during maternal or paternal exposures to study drug should be reported. Data on fetal outcome and breastfeeding are collected for regulatory reporting and drug safety evaluation.

Study site personnel will record the occurrence and nature of each patient's preexisting conditions, including clinically significant signs and symptoms of the disease under treatment in the study.

After the ICF is signed, site personnel will record the occurrence and nature of any AEs and any change in the preexisting condition(s). All AEs related to protocol procedures are reported to Lilly or its designee.

Investigators will be instructed to report to Lilly or its designee their assessment of the potential relatedness of each AE to protocol procedure and study drug via CRF, electronic data entry or other designated data transmission methods.

Patients will be evaluated for AEs at each visit and will be instructed to call their physician to report any AEs between visits.

The NCI CTCAE v4.0 will serve as the reference document for choosing appropriate terminology for, and grading the severity of, all AEs and other symptoms. For AEs without matching terminology within the NCI CTCAE v 4.0 criteria, the investigator will be responsible for selecting the appropriate system organ class (SOC) and assessing severity grade based on the intensity of the event.

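### Protocol 9.2.2 points to criteria for counting myelosuppression as a DLT, but none is hematological, so LY3039478-related cytopenia counts only by discretion

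*Protocol*

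**What the plan says.** Protocol 9.2.2 begins from the fact that disease-related myelosuppression is typical in T-ALL/T-LBL, and states that "myelosuppression will not be included in the definition of a DLT, unless it fits the criteria outlined below". A DLT must be an adverse event in Cycle 1 that is at least possibly related to LY3039478. It must also meet one of two criteria:

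- Grade 3 or higher nonhematological toxicity, with seven listed exceptions.
- "any other significant toxicity deemed by the primary investigator and Lilly clinical research personnel to be dose limiting". The one example given is a possibly related toxicity that forces withdrawal in Cycle 1.

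The DLET definition in the same section uses the same criteria for later Phase 1 cycles and for all Phase 2 cycles.

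Protocol 10.3.1 says of Grade 3 or 4 cytopenias that "these cytopenias will not be considered AEs for the purpose of this study, unless the investigator classifies them as AEs based on clinical circumstances".

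On the drug's history, Protocol 5.1.5 records that "Thrombocytopenia was identified as a DLT in a few Phase 1 patients". Protocol 5.1.6 says that the DLTs at 20, 30 and 60 mg in JJCA "were thrombocytopenia Grade 4 in 1 patient in each dose group". It lists Grade 3 nausea and Grade 3 asthenia as DLTs at 100 mg and gives the JJCA MTD as 75 mg. JJCB starts at 50 mg.

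**The concern.** The pointer in 9.2.2 promises criteria under which myelosuppression would count, and the list beneath it gives no grade, duration, bleeding or marrow rule for cytopenia. SAP 6.14.2.1 does not supply one either. The stated reason for the exclusion is cytopenia caused by the disease, but the exclusion covers all myelosuppression. It applies equally to T-LBL, which Protocol 5.1.1 separates from T-ALL by marrow infiltration below 25%.

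DLT status has several consequences. The DLT count updates the escalation model, bears on the 33% limit that defines the MTD (9.2.2), and decides whether a cohort may be enlarged: "If 1 patient experiences a DLT, then additional patients can be enrolled to that cohort" (9.2.1). For the patient, a DLT or DLET suspends treatment for the rest of the cycle (9.4.1) and leads to a lower dose afterwards (9.4.2). A toxicity already seen with this drug at doses around the JJCB starting dose would by default enter none of these, and different sites could count the same event differently.

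**Working it through.** **1. Follow one event through the text.** Take Grade 4 thrombocytopenia in Cycle 1, possibly related to LY3039478.

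- Is it an adverse event? Under 10.3.1, by default no. The investigator has to classify it as one.
- If classified, does it meet the first DLT criterion? No, because it is hematological. The seven exceptions (nausea/vomiting/constipation, electrolytes, hyperglycemia, hypertension, tumor lysis, diarrhea, transaminases) only narrow that criterion and do not address cytopenia.
- Does it meet the second criterion? Only if the investigator and the sponsor both deem it dose limiting. Withdrawal in Cycle 1 is the only example offered.

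The between-cycle rule does not close the gap: "Before the start of each cycle, nonhematological toxicities (except alopecia and fatigue) must resolve to baseline" (9.4.2).

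**2. Reproduce the plan's figure.** Protocol 5.1.6 reports 39 patients with validated data at 2.5 to 60 mg and 3 patients with related Grade 4 thrombocytopenia. 3/39 = 7.7%, as stated. One DLT at each of 20, 30 and 60 mg gives the same 3 patients. All 3 counted as DLTs in JJCA. None meets the nonhematological criterion of JJCB.

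**3. Exact interval.** The Clopper-Pearson limits solve P(X ≥ 3 | n = 39, p) = 0.025 and P(X ≤ 3 | n = 39, p) = 0.025. The results are 1.62% and 20.87%.

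**4. Chance of an uncounted event in one cohort.** Assume that the pooled rate c applies in JJCB, that patients are independent, and that the discretionary item captures none. For a cohort of 3, the chance of at least one event is 1 − (1 − c)³.

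| c | 1 − (1 − c)³ |
|---|---|
| 0.0162 | 1 − 0.9838³ = 0.05 |
| 0.0769 | 1 − 0.9231³ = 0.21 |
| 0.2087 | 1 − 0.7913³ = 0.50 |

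In a cohort with no other DLT, one such event is the difference between 0/3 and 1/3, the point at which 9.2.1 provides for adding patients.

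**5. Compare with the 33% limit.** The pooled rate (7.7%) and its upper limit (20.9%) both lie below 33%. Protocol 5.1.6 also lists one patient each with Grade 3 colitis, asthenia, weight loss and anorexia, and one with Grade 4 lipase. If all five had counted, in different patients, the total would be (3 + 5)/39 = 20.5%. Grade 3 hypophosphatemia (5 patients) is left out because 9.2.2 exempts electrolyte disturbance that is controlled and lasts under 5 days. These are pooled figures that include low doses, so they neither show nor exclude an effect at any one dose.

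**The case against.** The other side has good points, and most of them stand.

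- **The pointer is not empty.** The discretionary item is not confined to nonhematological events, and related cytopenia that forces Cycle 1 withdrawal fits its example. A reader might infer that cytopenia can never be a DLT. The text does not say that.
- **Thrombocytopenia did not stop JJCA.** Escalation continued to 100 mg, and the DLTs listed there were nonhematological. A reader might infer that the MTD in JJCB will be set too high. Single events at three doses, without dose-specific denominators, do not support that.
- **Other rules act on cytopenia.** Laboratory measurements are reviewed before each escalation (12.2.14). After omission for a non-DLT toxicity, dosing resumes only once the toxicity has resolved to baseline (9.4.1). More than 7 omitted doses in a cycle for tolerability calls for dose reduction, and a patient not recovered from toxicity within 21 days should be discontinued (9.4.2). That last clause is not expressly limited to nonhematological toxicity, although it follows a sentence that is. It would therefore be wrong to say that every such event in Phase 2 escapes mandatory dose action. The omission trigger is a late one, however: dosing three times a week gives 12 doses per cycle.
- **Many patients may be cytopenic at entry.** Protocol 7.1 sets no platelet minimum, and 10.3.1 expects Grade 3 or 4 cytopenia in relapsed T-ALL. A Grade 4 count may be neither new nor attributable to the drug, so the JJCA rate may not transfer.
- **The escalation prior.** Because the prior is based on JJCA DLT rates (9.2.1), a reader might infer that prior and trial data use conflicting definitions. The derivation is in a separate simulation plan (SAP 6.14.2.1), so this cannot be judged. If the three JJCA events are kept, they make the prior more cautious.

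These safeguards limit harm to the patient. They do not make the event count as a DLT, and they do not supply the missing criterion.

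**Conclusion.** The point holds as a gap in the DLT definition. Read as written, 9.2.2 and 10.3.1 together leave related Grade 4 thrombocytopenia uncounted by default, although it was the only DLT listed in JJCA at or below 75 mg. Excluding disease-related cytopenia is sensible. What is missing is a rule for cytopenia that the disease and the baseline count do not explain.

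The size is illustrative: about a 21% chance of at least one uncounted event in a 3-patient cohort, 5% to 50% over the confidence interval. It assumes that the rate pooled over 2.5 to 60 mg applies at JJCB doses and in this population, and that discretion captures none of the events. The second assumption is the least favorable case for capture, so the result does not bound the event rate itself. No change in the MTD is shown or claimed. The change should be made because it is inexpensive and concerns patient safety, but the existing safeguards keep this from being a fundamental fault.

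**What to change.** 1. In Protocol 9.2.2, add a DLT/DLET criterion for Grade 4 thrombocytopenia or neutropenia that is at least possibly related to LY3039478, is not explained by leukemic marrow involvement or baseline cytopenia, and persists for a stated duration. The sponsor's clinicians should set the duration so that the scheduled counts can show it within the 28-day window. Attachment 1 has Phase 1 Cycle 1 hematology on Days 1, 8, 15 and 22. A 7-day persistence can thus be shown for an event first seen by Day 15, but one first seen on Day 22 would need a stated rule. After Cycle 1 the counts are less frequent, so the DLET wording should allow for that.
2. In Protocol 10.3.1, state that such events are recorded as adverse events, so that the first gate does not depend on the investigator's choice.

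For T-ALL, the marrow examinations already planned at baseline and on Day 28 (−3 days) of Cycle 1 can support attribution. The cost is a few lines of protocol text, with no change to the planned sample size or visits. The downside is that judgement about attribution remains, especially in T-LBL where no Cycle 1 marrow is scheduled, and that escalation may be slower or cohorts larger if such events occur.
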